## 7.2. Detailed Study Procedures

### VISIT 0

Visit 0: Pre-Screening			
Step	Procedure	Details	
0.1	Phone/electronic Consent	Obtain Consent from the subject utilizing an EC-approved consent for use of CLDEQ-8 in the study	
0.2	Pre-screen CLDEQ-8 Questionnaire	The subject will respond to the CLDEQ-8 
 
If CLDEQ-8 sum score is equal or greater than 20, then schedule Visit 1 for screening
 
If CLDEQ-8 sum score is lower than 20, subject is not eligible for further screening
 
	

### VISIT 1

Subjects should be asked to attend Visit 1 wearing their habitual contact lenses. Subjects should bring some confirmation of their lens type (e.g. lens box, blister, etc.) if this information has not already been provided.

Visit 1: Screening			
Step	Procedure	Details	
1.1	Statement of Informed Consent	Each subject must read, understand, and sign the Statement of Informed Consent before being enrolled into the study. The Principal Investigator or his/her designee conducting	Informed Consent

		the informed consent discussion must also sign the consent form.  Note: The subject must be provided a signed copy of this document.	
1.2	Demographics	Record the subject's date of birth, gender, race and ethnicity.	
1.3	Medical History and Concomitant Medications	Questions regarding the subjects' medical history and concomitant medications.	
1.4	Habitual Lenses	Questions regarding the subject's habitual lens type and parameters.	
1.5	CLDEQ-8 Questionnaire	The Investigator will enter the subject's responses to the Pre-screen CLDEQ-8 Questionnaire on the database.	██████████
1.6	Eligibility after Screening	All responses to Screening Inclusion Criteria questions must be answered "yes" and all responses to Exclusion Criteria must be answered "no" for the subject to be considered eligible.	

Visit 1: Baseline			
Step	Procedure	Details	██████████
1.7	Visual Acuity	Record the distance high contrast visual acuity to the nearest letter (OD and OS) with their habitual contact lenses in place.  (Inclusion criterion: LogMAR of 0.20 or better in both eyes)	Eurolens Research SOP # 12a
1.8	Slit Lamp Biomicroscopy	Efron Slit Lamp Classification Scale will be used to grade the findings and determine eligibility.  If there are any Grade 3 or higher slit lamp finding, the subject is ineligible to continue at this time, but may return up to one additional time to determine eligibility. If discontinued a final examination must be completed.  If the clearance of the fluorescein needs to be expedited, preservative-free rewetting drops or saline may be instilled.	Eurolens Research SOP #13
1.9	Eligibility after Baseline	All responses to Inclusion Criteria questions must be answered "yes" and all responses to Exclusion Criteria questions must be	

Visit 1: Baseline			
Step	Procedure	Details	
		answered “no” for the subject to be considered eligible.	
1.10	VAS scale dispensing	Subjects will be issued with VAS scales to record subjective comfort on the days of Visit 2-4. Subjects will receive instructions for completion.	Appendix E
1.11	Exit VA	Record subjects’ distance high contrast visual acuity to the nearest letter (OD and OS) with their habitual spectacle correction in place (or unaided if applicable).	EuroLens Research SOP # 12a
1.12	Randomization	Subjects will be assigned a line on the randomization scheme.	
1.13	End of Visit 1	Subject discharged and asked to return for Visit 2. Subjects can leave wearing contact lenses, spectacles or unaided as determined by the investigator.	

#### VISITS 2 - 4

Subject should attend Visits 2-4 having worn their habitual contact lenses for 14 ± 2 hours having had a washout period of 1 – 14 days from the previous visit.

Pre-Visit 2-4 (at home)			
Step	Procedure	Details	
2.1	Subjective comfort	Subjective comfort scores (vertical VAS scale) will be collected for each eye immediately prior to lens application.  A text message will be sent the day before to remind subjects to complete the VAS scales immediately prior to and 5 minutes after lens application	
2.2	Lens application	Subjects will apply their habitual contact lenses. The time of lens application will be recorded on the VAS scale.  A text message will be sent to subjects to confirm lens application. Subjects will be asked to reply ‘yes’ if they have applied the contact lenses or ‘no’ if they have not. If they have not applied, the visit can be rescheduled to a different day for a maximum of two further occasions.	
2.3	Subjective comfort	Subjective comfort scores (vertical VAS scale) will be collected for each eye after 5 minutes of lens settling.	

Visit 2-4 (in clinic after 14 ± 2 hours of lens wear)			
Step	Procedure	Details	
2.4	Adverse Events and Concomitant Medications Review	Review any changes to the subject's medical history or concomitant medications from the previous study visit. Record any changes, and any adverse events.	
2.5	Wearing Time	Record the wearing time since application and comfortable wearing time.	
2.6	Subject Reported Ocular Symptoms	Subjects will respond to a verbal open-ended symptoms questionnaire.	
2.7	Collection of VAS scale	The investigator will collect the comfort VAS scales and will enter the scores on the database.  If subjects have not completed the VAS scales, the visit can be rescheduled to a different day for a maximum of two further occasions.	
2.8	Entrance Visual Acuity	Record the distance high contrast visual acuity to the nearest letter (OD and OS) with their habitual contact lenses.	Eurolens Research SOP #12a
2.9	Slit Lamp Biomicroscopy (white light only)	Efron Slit Lamp Classification Scale will be used to grade the findings.  If any of these slit lamp findings are Grade 3 or higher, it will be recorded as an Adverse Event.	Eurolens Research SOP #13
2.10	Subjective Lens Fit Assessment	Lens fit will be recorded according to a -2 to +2 integer scale for each of the following criteria:  Horizontal centration: -2 = Extremely Nasal -1 = Slightly Nasal 0 = Optimum +1 = Slightly Temporal +2 = Extremely Temporal  Vertical centration: -2 = Extremely Superior -1 = Slightly Superior 0 = Optimum +1 = Slightly Inferior +2 = Extremely Inferior  Coverage: -2 = Extremely Inadequate -1 = Slightly Inadequate 0 = Optimum	

		
+1 = Slightly Excessive +2 = Extremely Excessive
 
Movement -2 = Extremely Inadequate -1 = Slightly Inadequate 0 = Optimum +1 = Slightly Excessive +2 = Extremely Excessive
	
2.11	Subjective comfort	Subjective comfort scores (vertical VAS scale) will be collected for each eye.	██████████
2.12	Right eye Application of topical treatment	
One ocular region (upper lid margin, lower lid margin or cornea) of the right eye will be anesthetized or will receive a saline placebo treatment, based on the randomization scheme.
 
The procedures will take place with the subject's lenses in situ when the lid margins are treated. When the cornea is anesthetized, the subject's habitual lens will be removed and immediately dosed with the anesthetic as outlined in SOP #54. The lens will not be spun to removed excess liquid and will not be soaked in any solution prior to re-insertion. The dosing/re-application procedure should take place as quickly as possible to avoid the lens from dehydrating excessively.
 
If any problems with the application of the treatment occur, subjects are eligible to repeat the visit on another day only once.
	Eurolens Research SOP #54
2.13	Right eye Subjective comfort	
Subjective comfort scores (vertical VAS scale) will be collected for the right eye after 5 and 10 minutes post-treatment.
 
For the cornea, the contact lens is removed and then reapplied as part of the treatment application procedures. Comfort scores will also be collected immediately (ideally within 30 seconds) after lens removal prior to treatment application.
	██████████
2.14	Left eye Application of topical treatment	The same ocular region (upper lid margin, lower lid margin or cornea) of the left eye will be anesthetized or will receive a saline placebo treatment, based on the randomization scheme.	Eurolens Research SOP #54

		
The procedures will take place with the subject's lenses in situ when the lid margins are treated. When the cornea is anesthetized, the subject's habitual lens will be removed and immediately dosed with the anesthetic as outlined in SOP #54. The lens will not be spun to removed excess liquid and will not be soaked in any solution prior to re-insertion. The dosing/re-application procedure should take place as quickly as possible to avoid the lens from dehydrating excessively.
 
If any problems with the application of the treatment occur, subjects are eligible to repeat the visit on another day only once.
	
2.15	Left Subjective comfort	
Subjective comfort scores (vertical VAS scale) will be collected for the left eye after 5 and 10 minutes post-treatment.
 
For the cornea, the contact lens is removed and then reapplied as part of the treatment application procedures. Comfort scores will also be collected immediately (ideally within 30 seconds) after lens removal prior to treatment application.
	██████████
2.16	Contact lens removal	Contact lenses will be removed and discarded.	
2.17	Exit Slit Lamp Biomicroscopy (Visits 2-3 only)	
Efron Slit Lamp Classification Scale will be used to grade the findings.
 
Adverse events shall be documented and followed to resolution.
 
If the clearance of the fluorescein needs to be expedited, preservative-free rewetting drops or saline may be instilled.
	Eurolens Research SOP #13
2.18	Exit VA (Visits 2-3 only)	Record subjects' distance high contrast visual acuity to the nearest letter (OD and OS) with their habitual spectacle correction in place (or unaided if applicable).	Eurolens Research SOP # 12a
2.19	End of Visit (Visits 2-3)	Subject discharged and asked to return for next visit. Subjects can leave wearing spectacles or unaided as determined by the investigator.	

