### Secondary Hypotheses

1. Post-treatment subjective scores of comfort (VAS scale) for eyes with the cornea anesthetized are superior to eyes with the upper or lower lid margins anesthetized.
2. Comfort change from pre-treatment for eyes with the cornea anesthetized is superior to eyes with the upper or lower lid margins anesthetized.
3. Subjective scores of comfort (VAS scale) at lens removal are equivalent to baseline levels (i.e. immediately prior to lens application in the morning) when the cornea is anesthetized. An equivalence margin of 10 points will be used.

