### 1. Cornea

Two methods for anaesthetising the cornea can be used:

a. 'Contact lens' method:

- i. A soft contact lens is removed from its blister packaging and placed into a lens holder (from a barrel contact lens case) and centrifuged for 2 seconds using a custom low-speed centrifuge to remove surface packaging solution from the contact lens surface.
- ii. A 10 µl drop of anaesthetic is dispensed onto the back surface of the contact lens using an automated micropipette and a sterile pipette tip.
- iii. The subject is asked to face downwards.
- iv. The upper and lower eyelids are retracted using fingers or an Eyegenie (Eyelid retractor).
- v. The investigator applies the dosed contact lens directly onto the cornea, whilst the eyelids are held apart for a further minute to allow the anaesthetic to be absorbed and avoid spreading to other parts of the ocular surface.

- vi. The contact lens is removed, the eyelids are then released and the subject is allowed to blink normally.
- b. 'Drop' method:
- i. The subject is asked to lift the chin and lean the head backward during the procedure.
  - ii. The upper and lower eyelids are retracted using fingers or an Eyegenie (Eyelid retractor).
  - iii. A 3µl drop of anaesthetic is dispensed onto the central cornea using an automated micropipette and a sterile pipette tip. Flexible silicone tubing will be attached to the pipette tip.
  - iv. The eyelids are held apart for a minute to allow the anaesthetic to be absorbed and avoid spreading to other parts of the ocular surface.
  - v. The eyelids are then released and the subject is allowed to blink normally.

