## 2. Eyelid margins

This procedure can be carried out on the upper and lower eyelid margins.

- a. A soft contact lens is applied to the eye to shield the cornea.
- b. A cotton bud is manipulated until a fine thread is created at the tip.
- c. This tip is saturated with the anaesthetic.
- d. The saturated cotton bud tip is then used to 'brush' the full length of the upper or lower lid margin for 30 seconds.
- e. The upper lid margin should be completely everted whilst the lower lid margin needs only to be partially everted.
- f. The eyelid is kept fully or partially everted (whichever is relevant) for 30 seconds.
- g. A second application of anaesthetic using the saturated cotton bud is performed for 30 seconds.
- h. The eyelid is kept fully or partially everted (whichever is relevant) for a further minute to allow the anaesthetic to be absorbed and avoid spreading to other parts of the ocular surface.
- i. The contact lens is removed, the eyelids are then released and the subject is allowed to blink normally

The anaesthetic effect lasts between 15 minutes and one hour. The subject should be advised not to wear their own contact lenses for at least two hours after the procedure..

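### The cornea-minus-lid contrasts in section 14.6 mix the anesthetic effect with a difference in procedure, and the plan never tests the placebo-corrected difference

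*Combined protocol and SAP*

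**What the plan says.** Secondary hypothesis 1 (section 2.3) is that post-treatment comfort scores "for eyes with the cornea anesthetized are superior to eyes with the upper or lower lid margins anesthetized". Secondary hypothesis 2 makes the same claim for change from pre-treatment. Section 14.6 tests each through the two-sided 95% CI for the least-squares mean difference, cornea minus upper or lower lid margin. One lower limit above 0 out of two is enough. No saline term appears, and 14.6 names no model of its own.

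The visits differ in more than the region numbed:

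- **Lid visits.** Treatment is done with the "lenses in situ when the lid margins are treated". SOP #54 brushes "the full length of the upper or lower lid margin for 30 seconds", twice. On eversion it says: "The upper lid margin should be completely everted whilst the lower lid margin needs only to be partially everted".
- **Corneal visit.** The "habitual lens will be removed and immediately dosed with the anesthetic as outlined in SOP #54". Steps 2.13 and 2.15 confirm that "the contact lens is removed and then reapplied as part of the treatment application procedures". SOP #54 has the dosed lens placed on the cornea "whilst the eyelids are held apart for a further minute to allow the anaesthetic to be absorbed".

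All this comes before the 5- and 10-minute scores. The pre-treatment score is step 2.11 ("Subjective comfort scores (vertical VAS scale) will be collected for each eye"), before any of it. At every visit the fellow eye receives saline at the same region.

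Both models in 14.5 list treatment and region as fixed effects, with sequence, period and carryover terms (and time event in the first). Neither lists treatment-by-region. Yet 14.5 concludes superiority over placebo region by region.

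**The concern.** Region and procedure never vary separately, and randomizing the order of regions does not part them. A corneal win under 14.6 would naturally be read as showing that numbing the cornea relieves end-of-day discomfort more than numbing a lid margin. It could also reflect a short break in wear, liquid on the lens, or irritation from lid brushing. If putting a worn lens back is uncomfortable, a real corneal advantage could be masked. The sponsor itself treats lens removal as relevant to comfort: its effect is the secondary objective. Locating the source of discomfort is the purpose of the study, so the attribution matters.

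**Working it through.** **1. The plan's own figure.** Section 14.2 gives power only for the primary tests. With 15 subjects, SD of a difference = SD × sqrt(2(1 − ICC)) and a paired t-test on 14 df, all 18 cells of Table 3 reproduce at one-sided 0.05. For a difference of 7.5, SD 15 and ICC 0.8 the result is 0.897, as printed. At two-sided 0.05 that cell is 0.812. The 14.6 tests use two-sided 95% limits, so 2.5% per side applies below.

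**2. What each contrast estimates.** Let d be the extra effect of corneal over lid anesthesia, and h the comfort difference due to procedure (corneal minus lid).

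| Contrast | Expected value |
|---|---|
| Cornea minus lid, anesthetized eyes | d + h |
| Cornea minus lid, saline eyes | h |
| Placebo-corrected: (anesthesia − saline at cornea) − (anesthesia − saline at lid) | d |
| Region difference from the model as listed (no interaction, eyes averaged) | d/2 + h |

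Subtracting step 2.11 leaves d + h, because that score precedes the procedure. If h differs between eyes (h_A numbed, h_S saline), the corrected contrast estimates d + h_A − h_S.

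**3. Inputs.** From 14.2: n = 15, SD 15 or 20, single intraclass correlations of 0.4, 0.6 and 0.8. Assumed: h from 0 to 10 points, and correlations of 0.6 between visits and 0.8 between fellow eyes at one visit. A common 0.6 is shown as well.

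**4. Standard errors at SD 15.**

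- Planned: sqrt(2 × 225 × 0.4 / 15) = 3.46.
- Corrected: sqrt(4 × 225 × 0.2 / 15) = 3.46 at 0.8/0.6, or sqrt(4 × 225 × 0.4 / 15) = 4.90 at a common 0.6.
- 95% half-width for the saline-eye estimate of h: 2.145 × 3.46 = 7.4 points; at SD 20, 2.145 × 4.62 = 9.9.

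**5. Chance of concluding corneal superiority on at least one lid when d = 0 and h acts equally on both eyes** (simulation, 40,000 runs, paired-t limits as an approximation to the mixed model, correlations 0.8/0.6):

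| h | Planned, SD 15 | Planned, SD 20 | Corrected, either SD |
|---|---|---|---|
| 0 | 0.05 | 0.05 | 0.05 |
| 5 | 0.41 | 0.28 | 0.04–0.05 |
| 7.5 | 0.69 | 0.48 | 0.05 |
| 10 | 0.90 | 0.70 | 0.04–0.05 |

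Across SD 15–20 and correlations 0.4–0.8, the planned test gives 22–65% at h = 5 and 54–99% at h = 10.

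**6. Masking.** At d = 10, h = −5, SD 15, the planned contrast succeeds 0.41 and the corrected one 0.89.

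**7. When h is unequal (d = 0, SD 15).** If re-insertion discomfort of 5, 7.5 or 10 points is felt only by the un-numbed corneal eye, the corrected contrast errs 0.41, 0.70 and 0.90, and the planned one stays at 0.05. If a 5-point benefit occurs only in the numbed corneal eye, each errs 0.41.

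**8. The model read literally (SD 15, 0.8/0.6).** The pooled region contrast errs 0.50 at d = 0, h = 5. It succeeds only 0.50 at d = 10, h = 0, where the anesthetized-eye contrast succeeds 0.89.

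**The case against.** The 14.6 contrast answers the hypotheses as worded: they compare treated eyes, and for eyes as treated the comparison is sound. That stands, so the issue is attribution.

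A reader might infer that the saline eyes go unused, or that the study cannot separate the two effects. The documents do not support that. Section 14.5 tests anesthesia against saline for each region. A procedure that helped both corneal eyes equally would leave the corneal anesthesia-minus-saline difference near zero. Section 14.1 also plans summaries and allows exploratory analysis. What is missing is the formal difference between the regional effects; comparing separate regional conclusions is not a test of that difference.

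The size of h is unknown. The upper value of 10 equals the largest superiority effect in 14.2, and discomfort may fade before the 5- and 10-minute scores; the plan itself allows 5 minutes for morning settling. That stands: the table shows sensitivity, not an expected error rate.

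Equal procedural effects in numbed and un-numbed eyes are doubtful when the treatment is an anesthetic. That stands too, and is why the corrected contrast should accompany the planned one rather than replace it.

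The interaction may be implied by the region-specific tests. If so, writing it down changes nothing; if not, those tests cannot be obtained from the listed terms.

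Lids are held at both kinds of visit, so only eversion, brushing and lens handling differ. SOP #54 ends the lid procedure with lens removal, but the study steps keep the lens in and remove it at 2.16, after scoring.

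**Conclusion.** The concern holds as a matter of attribution and model specification. A procedural difference enters the 14.6 contrasts in full, the change score does not remove it, and the plan has no test of the placebo-corrected difference. The possible distortion runs from none at h = 0 to a near-certain corneal win at h = 10 under the most favorable correlation, with h entirely assumed.

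Two further readings go too far. A corneal win cannot be called an artefact, since neither the sign nor the size of h is documented. Nor are primary hypotheses 1 and 2 confounded by procedure, because both eyes have the same region treated at a visit. They are not wholly untouched either: without treatment-by-region, the listed model gives one common anesthesia effect, so the region-specific primary tests need that term.

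This is a worthwhile improvement to secondary analyses in a pilot study. It does not invalidate the design.

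**What to change.** 1. Add treatment-by-region to both 14.5 models, and define the 14.6 cornea-minus-lid contrast on the anesthetized eyes.
2. Keep that contrast as the test of secondary hypotheses 1 and 2. Beside it report, each with a 95% CI, the placebo-corrected contrast and the saline-eye cornea-minus-lid difference.
3. Describe a corneal win as an effect of the whole corneal procedure unless the placebo-corrected estimate supports an anesthetic effect. State that the correction assumes equal procedural effects in numbed and un-numbed eyes.

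A rigid rule that both lower limits exceed 0 for the same lid is not recommended. At d = 10, h = −5, SD 15 it succeeds 0.38, so it does not recover a masked advantage. It still errs 0.21 if a 5-point benefit occurs only in the numbed eye.

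**Cost.** One model term, two reported contrasts and a sentence on interpretation; no added subjects, visits or data. The anesthetized-eye test is unchanged. The corrected contrast may be less precise: at d = 10, h = 0, SD 15 it succeeds 0.90 at correlations 0.8/0.6 but 0.65 at a common 0.6, against about 0.89 for the planned one. At SD 20 the figures are 0.70 and 0.44, against 0.70. The estimate of h will be rough, and the correction is itself biased if the procedure acts differently on numbed eyes.

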## FINAL EVALUATION

The final evaluation will ordinarily take place immediately following the last scheduled follow-up visit per the study protocol. It may also take place at any point the subject discontinues the study or is terminated from the study.

Final Evaluation			
Step	Procedure	Details	
F.1	Final Exam Form	Indicate if the subject completed the study successfully. If subject discontinued from the study, indicate the reason.	
F.2	Exit Slit Lamp Biomicroscopy	Efron Slit Lamp Classification Scale will be used to grade the findings.  Adverse events shall be documented and followed to resolution.  If the clearance of the fluorescein needs to be expedited, preservative-free rewetting drops or saline may be instilled.	Eurolens Research SOP #13
F.3	Exit Visual Acuity	Record subjects' distance visual acuity to the nearest letter (OD and OS) with their habitual spectacle correction in place (or unaided if applicable).	Eurolens Research SOP # 12a

### 7.3. Unscheduled Visits

If, during the investigation, a subject requires an unscheduled visit to the clinical site, the following information will be collected at a minimum:

- Chief complaint prompting the visit. If the reason is an adverse event, the applicable eCRF for the adverse event must be completed and subject record completed as appropriate
- Date and time of the visit and all procedures completed at the unscheduled visit
- Review of adverse event and concomitant medications
- Documentation of any test article dispensed or collected from the subject, if applicable
- Slit lamp findings (using the Slit Lamp Classification Scale)

If the Investigator withdraws a subject from the study, the final study visit case report forms must be completed indicating the reason(s) why the subject was withdrawn. The subject record must be completed documenting the date and primary reason for withdrawal and the study CRA notified.

Any ocular and non-ocular Adverse Events that are ongoing at the time of the study visit will be followed by the Investigator, within licensure, until they have resolved, returned to pre-treatment status, stabilized, or been satisfactorily explained. If further treatment i.e., beyond licensure is required, the subject will be referred to the appropriate health care provider.

The following information will be collected during an unscheduled visit (when applicable)

Unscheduled Visit			
Step	Procedure	Details	
U.1	Chief Complaints	Record the subject's chief complaints for reasons for the unscheduled visit.	
U.2	Adverse Events and Concomitant Medications Review	Review any changes to the subject's medical history or concomitant medications from the previous study visit. Record any changes, and any adverse events.	
U.3	Slit Lamp Biomicroscopy	Efron Slit Lamp Classification Scale will be used to grade the findings. If the clearance of the fluorescein needs to be expedited, preservative-free rewetting drops may be instilled.	Eurolens Research SOP # 13
U.4	Exit Visual Acuity	Record the exit distance visual acuity to the nearest letter (OD and OS) with their habitual spectacle correction in place (or unaided if applicable).	Eurolens Research SOP # 12a

